1.2 Study Design

The study population is characterized by the following main inclusion criteria:

- 18 to 65 years of age inclusive
- Diagnosis of AD for ≥ 1 year
- Moderate-to-severe AD at randomization visit as defined by
 - EASI score ≥ 16 ,
 - BSA affected by $AD \ge 10\%$,
 - vIGA-AD score \geq 3, and
 - Peak Pruritus 0-10 NRS \geq 4 (average score of the daily scores of the 7 days before randomization, with \geq 4 scores required).
- Documented history (within 6 months prior to the first screening visit) of inadequate response to treatment with topical corticosteroids (TCS), or if TCS are medically not advisable (e.g., due to important side effects or safety risks)
- Stable amount of emollient applied to skin over the whole body twice daily for at least the 7 consecutive days before the randomization visit
- Body mass index (BMI) within the range of 18.5 to 35.0 kg/m2 (inclusive)

The design of the study is as follows:

Study phase:	Phase 2a (Proof of concept)		
Study population:	Adult patients with moderate-to-severe atopic dermatitis		
Design:	Parallel group design		
Blinding:	Double-blind		
Placebo controlled:	Yes		
Randomized:	Yes		
Strata:	No		
Countries:	7 countries, multicenter		
Treatment:	Zabedosertib 120 mg		
	Placebo		
Frequency of treatment:	Twice daily		

Route of treatment:Oral intakeDuration of treatment:12 weeks (84 days)

A total of 72 participants are planned to be randomly allocated to 1 of the 2 treatment groups with a 2:1 allocation ratio to achieve a total of 57 participants valid for efficacy analysis:

zabedosertib at a dose of 120 mg BID:48 randomized / 38 valid for the efficacy analysisMatching placebo BID:24 randomized / 19 valid for the efficacy
analysis.

The study consists of

- a 28-day screening period (Visits 1 and 2),
- a 12-week intervention period consisting of 5 visits (Visits 3, 4, 5, 6, and 7),
- and a 4-week follow-up (FU) period with one visit (Visit 8).

Thus, the total study duration per participant will be 17 to 20 weeks (approximately 140 days), with 8 study visits at intervals of 8 to 28 ± 3 days.

The primary analysis will be performed after database release.

2. Statistical Hypothesis

The primary efficacy endpoint is achievement of 75% reduction from baseline in the EASI (EASI 75 response) at Week 12 (Day 84, EOT).

Let π_{BAY} and π_{Plac} be the responder rate with respect to EASI 75 after zabedosertib and placebo, respectively.

The statistical hypothesis is defined as follows:

 $\pi_{BAY} > \pi_{Plac}$ ('clinical activity' criterion),

i.e. that the EASI 75 responder rate after treatment with zabedosertib is higher than after placebo.

The study will be evaluated using Bayesian statistics, which allows to determine the posterior probability in favor of a hypothesis. Therefore, it is not needed to specify a pair of hypotheses. The statistical hypothesis will be considered accepted if the posterior probability for the hypothesis of interest is higher than 90%.

2.1 Multiplicity Adjustment

No adjustments for multiplicity are planned since this is an exploratory study.

CONFIDENTIAL

3. Analysis Sets

For the purpose of analysis, the following analysis sets are defined:

Analysis set	Description
Enrolled	All participants who signed the ICF.
All Randomized	All participants randomly assigned to study intervention
(RAND)	Participants will be analyzed according to the intervention they were randomized to.
Safety analysis set	All participants who took at least 1 dose of study intervention.
(SAF)	Participants will be analyzed according to the intervention they actually received.
Per protocol set (PPS)	All randomized participants who meet the following criteria: – have an EASI score at baseline
	 have an EASI score at Day 56 (Visit 6) or later or took rescue medication between Day 56 (Visit 6) and Day 84 (Visit 7) or took SoC (see Section 8.3 for definition of SoC) or discontinued study intervention due to lack of efficacy (at any time)
	(SoC medication use after early discontinuation due to other reasons will not qualify for the PPS)
	 showed compliance of at least 80% with study intervention between start of treatment and end of treatment or start of rescue medication at or after Day 56 (Visit 6), whatever comes first
	 showed compliance of at least 80% with study intervention during the last 4 weeks before end of treatment or start of rescue medication at or after Day 56 (Visit 6), whatever comes first.
	 are without validity findings with respect to the efficacy related entry criteria
	Participants will be analyzed according to the treatment they actually received.
Pharmacokinetic set	All participants who
PKS)	 were treated with zabedosertib,
	 have at least 1 valid zabedosertib plasma concentration sample,
	 are without protocol deviations, which would interfere with the evaluation of the PK data.
Full Analysis Set	All participants who
FAS)	– have an EASI score at baseline,
	 have a valid EASI score at Day 14 (Visit 4) or later or took rescue medication between Day 56 (Visit 6) and Day 84 (Visit 7) or took SoC (see Section 8.3 for definition of SoC) or discontinued study intervention due to lack of efficacy (at any time), (SoC medication use after early discontinuation due to other reasons will not
	qualify for the FAS)
	 took at least 1 dose of study intervention,
	- are without validity findings with respect to the main efficacy related entry criteria.
	Participants will be analyzed according to the treatment they actually received.
Biomarker analysis	All participants who
set (BAS)	 showed compliance of at least 80% with study intervention during the last 4 weeks before end of treatment
	 have at least 1 valid biomarker sample at baseline and post-dose (blood sample or biopsy),
	 are without validity findings, which would interfere with the evaluation of the biomarker data,
	- are without validity findings with respect to the main efficacy related entry criteria
	Participants will be analyzed according to the treatment they actually received.

Final decisions regarding the assignment of participants to analysis sets will be made during the blind review of study data and documented in the final list of important deviations, validity findings and assignment to analysis set(s). Any case-by-case decision concerning

validity will be taken during the blind review by persons without access to any individual post-dose efficacy data to avoid any potential bias.

Please also refer to Section 8.3 for the assessment of the intercurrent events "use of rescue medication", "use of systemic standard of care (SoC)", and "discontinuation of study intervention due to lack of efficacy" and Section 4.5.1 for the calculation of compliance used in the definition of the analysis sets FAS and PPS.

4. Statistical Analyses

4.1 General Considerations

4.1.1 General principles and data rules

The statistical evaluation will be performed by using the software SAS (release 9.4 or higher; SAS Institute Inc., Cary, NC, USA).

Continuous variables assumed to be normally distributed will be summarized using number of participants, mean, standard deviation, minimum, median, and maximum. Continuous variables assumed to be log-normally distributed will be summarized using number of participants, geometric mean, geometric standard deviation, geometric coefficient of variation, arithmetic mean, arithmetic standard deviation, arithmetic coefficient of variation, minimum, median, and maximum.

For categorical data frequency tables will be provided.

In general, summary statistics and frequency tables will be presented by treatment group, visit and time point (if applicable). Plots over time (if applicable) will also be presented by treatment group.

The baseline assessment will be the assessment at Day 1 (Visit 3). For all variables with exception of the efficacy variables (ClinRO and PRO data) the following applies: If the assessment on Day 1 (Visit 3) is missing, then baseline will be the last available assessment before first study drug intake (i. e. usually the screening assessment).

Summary statistics of continuous variables will be provided including absolute changes from baseline or percent changes from baseline. Absolute changes from baseline will be calculated as (post-dose value - baseline value) unless noted otherwise. Percent changes from baseline will be calculated as ((post-dose value - baseline value)/baseline value)*100 unless noted otherwise.

Efficacy variables at FU visits will only be evaluated by summary statistics, but they will not be included for statistical analyses such as Bayesian analyses, ANCOVA models and mixed models for repeated measures.

In case of replicate measurements for one visit mean values of the unrounded original values will be calculated by participant and visit. Summary statistics of these mean values will be provided.

Box plots will be displayed with whiskers of maximum 1.5 times the interquartile range (i. e. upper quartile minus lower quartile) above the upper quartile, and a distance of maximum 1.5 times the interquartile range below the lower quartile. All data points above or below the whiskers will be displayed as single data points.

For analytes which are below the lower limit of quantification (LLOQ), one half of the LLOQ will be used as an estimate for the respective value. However, means, standard deviations and coefficients of variation will only be calculated if at least 2/3 of the values are above (or equal to) the LLOQ. In tables showing mean values, where values below LLOQ are included in the calculation of mean values, these means will be marked. Corresponding tables and figures will get a footnote indicating that "Values below the lower limit of quantification were replaced by $\frac{1}{2}$ LLOQ if at least 2/3 of the values were >= LLOQ." Tables displaying minimum values will present "<LLOQ" as minimum. Similar rules will apply to data points above ULOQ. ULOQ will be used as an estimate for the respective values. Means, standard deviations and coefficients of variation for changes to baseline will only be calculated if there are at least 2/3 of the changes where the baseline and post-dose value are >= LLOQ and <=ULOQ.

The relative onset of adverse events with respect to treatment start will be expressed in days as follows (similar for relative end of adverse events):

- date of adverse event start minus date of treatment start for adverse events starting before treatment start
- date of adverse event start minus date of treatment start + 1 for adverse events starting on day of first treatment or later.

The duration of an AE will be calculated in days, i. e., the date of adverse event end minus the date of adverse event start +1.

The relative onset of prior/concomitant/posterior medication with respect to treatment start will be expressed in days as follows (similar for relative end of prior/concomitant/posterior medication):

- date of medication start minus date of treatment start for medications starting before treatment start
- date of medication start minus date of treatment start + 1 for medications starting on day of treatment start or later.

The duration of atopic dermatitis (in years) at baseline will be calculated as follows:

• (date of Day 1 (Visit 3) minus date of first diagnosis plus 1) / 365.25.

The age at onset (in years) will be calculated as follows:

• year of AD onset – year of birth.

Data from unscheduled measurements will be listed, but not included in summary statistics or frequency tables by visit unless specified otherwise (refer to Section 8.4 for handling of unscheduled measurements for efficacy variables).

Listings will be provided sorted by treatment group and participant identifier ('participant' and 'subject' will be used interchangeable in the tables, listings and figures and the CSR).

The following labels will be used for TLF outputs (unless indicated otherwise):

- Treatment groups:
 - Zabedosertib

Placebo,

• Visits:

Day -28 (Visit 1) Day -8 (Visit 2) Day 1 (Visit 3) Day 14 (Visit 4) Day 28 (Visit 5) Day 56 (Visit 6) Day 84 (Visit 7) FU visit.

All efficacy analyses will be performed on the PPS. In addition, the efficacy analyses will be performed on the FAS - unless otherwise indicated. Participants will be analyzed according to the treatment they actually received.

All safety analyses will be performed on the SAF, participants will be analyzed according to the treatment they actually received.

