8.3.3 Electrocardiograms

Single 12-lead ECG will be obtained as outlined in the SoA (see Section 1.3) or as clinically indicated using an ECG machine that automatically measures the ECG mean ventricular rate, PR, QRS, QT, and QTc intervals. Refer to Section 7.1.2 for QTcB withdrawal criteria and any additional QTcB readings that may be necessary.

ECG for each participant should be obtained using the same electrocardiograph machine whenever possible. To minimize variability, participants should remain in a resting position for at least 5-10 minutes prior to each ECG recording.

Quality of ECGs should be assessed immediately and in case of improper quality of an ECG another ECG(s) should be recorded to replace the improper ECGs, which would be documented as invalid by the investigator.

For each ECG, the investigator has to perform a thorough review that may result in ECG findings and an overall assessment (including clinical relevance) deviating from the automated device output.

Each ECG will be evaluated for the overall normality as follows:

- Normal
- Abnormal, clinically insignificant
- Abnormal, clinically significant.

Only the results of this local review will be entered as findings into the electronic CRF and any clinically relevant abnormality should be documented as an AE or SAE. ECG findings observed before first study intervention intake that reflects any previous cardiovascular

disease (e.g., atrial fibrillation, previous myocardial infarction or any abnormality in the electrical conduction system) should be documented as medical history.

ECG recordings will be kept as part of subjects file at the site as per site practice.

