9.3.3.2 Other Safety Endpoints

Laboratory values, ECG parameters and vital signs will be summarized descriptively by parameter including changes from baseline. Arithmetic mean plots including standard deviation over time will be presented.

For laboratory values shift tables will be provided (by time point including any time point) focusing on the frequency and percentage of participants with shifts from within normal range (or below normal range) at baseline to above normal range post-baseline and from within normal range (or above normal range) at baseline to below normal range post-baseline. Courses of laboratory values out of normal range at least at one time point will be listed by parameter and treatment group (abnormal values will be flagged with 'H' for high and 'L' for low).

A frequency table will be provided for ECG findings (by time point including any time point).

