4.1.2 Handling of missing data

Participants who discontinue the study prematurely (i. e. drop out) will not be replaced.

All data will be presented in the participant data listing as they are recorded on the Case Report Form (CRF), i. e., partially missing data will appear as such.

For participants who permanently discontinue the study intervention, an EOT visit (...) should be performed as soon as the study intervention has been discontinued. If the decision to stop the study intervention early is taken during a site visit, this visit becomes the EOT visit. The FU visit should be performed as planned after the last dose.

In general, data collected at early discontinuation visits will be handled as follows: If a valid value is available from the EOT visit and if the assessment time is in accordance with one of the upcoming visit windows (see Section 8.4.1 for visit windows) and is not assessed later than three days after last study drug intake, this value will be assigned to the respective visit for analysis. Values assessed at FU visits after EOT visits due to early discontinuation will be summarized together with FU visits after regular EOT visits at Day 84 (Visit 7) unless specified otherwise.

The data handling of efficacy data which might deviate from the procedure described above depending on intercurrent events is described in Section 8.4.

If parts of the start or stop date of an AE are missing (day, month or year) the relative onset of the AE with respect to treatment start and/or the duration of the adverse event will not be calculated.

Adverse events will be considered as treatment-emergent if they occur after the first study intervention intake and until 7 (calendar) days after last study drug intake.

To determine if an AE is treatment-emergent in case of missing or incomplete dates the following rules will be applied considering a "worst case" scenario, i. e. if it is possible that the AE is treatment emergent it will be considered as treatment-emergent:

- If the date of AE start is completely missing, the AE will be considered as treatmentemergent unless the stop date (or other information) suggests otherwise
- If the day of AE start is missing, but the month and year is known, the AE will be considered as treatment-emergent if the month of AE start is between the month of treatment start and the month of treatment end date plus 7 days (both included), unless the stop date of the AE (or other information) suggests otherwise

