- ALT or AST > 3 x ULN and INR > 1.5 x ULN (INR > 1.5 x ULN is only relevant if the participant is not on Vitamin K antagonist, new oral anticoagulants (NOACs) or heparin.)
- ALT or $AST > 5 \times ULN$ for more than 2 weeks
- ALT or $AST > 8 \times ULN$

Abnormalities with respect to neutrophil counts:

- Absolute neutrophil count < 500 cells/ μ L,
- Absolute neutrophil count 500 to < 1000 cells/ μ L,
- Absolute neutrophil count 1000 to < 1500 cells/ μ L.

Abnormalities with respect to creatinine kinase:

- Creatine kinase (CK) >ULN to < 5 x ULN,
- Creatine kinase (CK) 5 to 10 x ULN,
- Creatine kinase (CK) > 10 x ULN.

Vital signs

Vital signs will consist of single measurements of systolic blood pressure, diastolic blood pressure, pulse rate and body temperature. Vital signs including height (only summary statistics for the baseline value), weight and BMI will be summarized descriptively by parameter including absolute changes from baseline. Arithmetic mean plots including standard deviation over time will be presented. In addition, box plots including arithmetic means over time will be presented for changes from baseline. Individual plots over time will be generated.

Electrocardiogram

Single 12-lead ECG will be obtained locally.

ECG parameters (PR, QRS, QT, corrected QT intervals (according to Bazett's formula) and the ventricular rate) will be summarized descriptively by parameter including absolute changes from baseline. Arithmetic mean plots including standard deviation over time will be presented. In addition, box plots including arithmetic means over time will be presented for changes from baseline. Individual plots over time will be presented.

Furthermore, frequency tables will be presented for corrected QT intervals for absolute values with the following categories:

• >450 to 480 msec, >480 msec to 500 ms, >500 msec,

and absolute change from baseline with the following categories:

• >30 to 60 msec, >60 msec.

A frequency table will be provided for the ECG findings assessed by the investigator, and for overall interpretation of ECGs (normal; abnormal, clinically insignificant; abnormal, clinically significant).

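### The SAP's ECG-findings and QTc frequency tables state no any-time-point row, so their counts can miss the worst on-treatment ECG

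*SAP*

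**What the plan says.** **Protocol.** Changes in ECG parameters and the frequency of ECG findings are listed as a safety endpoint (Section 3.1). Section 9.3.3.2 sets the table: "A frequency table will be provided for ECG findings (by time point including any time point"). The Schedule of Activities places ECGs at screening, Day 14, Day 84 or end of treatment, and follow-up. Section 8.3.3 also foresees ECGs "or as clinically indicated using an ECG machine".

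**SAP, ECG tables.** Section 4.5.3 says: "A frequency table will be provided for the ECG findings assessed by the investigator, and for overall interpretation of ECGs". It also adds that "frequency tables will be presented for corrected QT intervals for absolute values with the following categories", namely above 450 to 480, above 480 to 500 and above 500 msec, with change categories of above 30 to 60 and above 60 msec. Neither passage mentions an any-time or worst-value row.

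**SAP, general rules.** Section 4.1.1 sets the layout: "In general, summary statistics and frequency tables will be presented by treatment group, visit and time point (if applicable"). It also says: "Data from unscheduled measurements will be listed, but not included in summary statistics or frequency tables by visit unless specified otherwise". The only exception it points to is for efficacy variables. Under Section 4.1.2 an early-discontinuation value is used "if the assessment time is in accordance with one of the upcoming visit windows", with windows taken from Section 8.4.1, and if it "is not assessed later than three days after last study drug intake, this value will be assigned to the respective visit for analysis".

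**SAP, declared changes.** Section 4.8 names two: the blinded sample size monitoring and the credible interval level. ECG is not among them.

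**The concern.** With two scheduled on-treatment ECGs, an abnormal reading may well come from an ECG taken off schedule: one done because it was clinically indicated, or the end-of-treatment ECG of someone who stopped early. An any-time-point row would pick these up. Without one, the by-visit rules leave out the first kind altogether and admit the second only under two conditions.

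At stake are the numbers of participants per arm with an ECG finding, with a clinically significant overall interpretation, or in a QTc category. Readers compare arms on these counts. If off-schedule ECGs are missing, a count can be too low, and the table would not show that anything is missing.

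**Working it through.** The plan gives no figure on this point, so there is none to reproduce. The check compares the rules and then counts days.

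**1. ECG against laboratory rules within SAP 4.5.3**

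| Output | Route for off-schedule values into the counts |
|---|---|
| Laboratory shift tables | Any-time-point entry kept, limited to the treatment phase |
| Treatment-emergent laboratory abnormalities | Counted over the whole period to 7 days after end of treatment |
| Liver screening plots | Each participant's maximum post-baseline value |
| ECG findings and overall interpretation | None stated |
| QTc absolute and change categories | None stated |

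For laboratory data, the same section provides what it leaves out for ECG.

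**2. Which ECGs enter a by-visit table**

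- Scheduled Day 14 and Day 84 ECGs: yes.
- Clinically indicated ECG on an unscheduled date: no, listed only (SAP 4.1.1).
- Early end-of-treatment ECG: only if it is inside a window and no later than three days after the last intake (SAP 4.1.2).

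**3. Days outside every window**

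Inputs are the windows in SAP Table 8-3: Days 10–18, 21–35, 49–63 and 76–92. An early end-of-treatment assessment is taken to fall on Days 1 to 83.

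- Covered: (18 − 10 + 1) + (35 − 21 + 1) + (63 − 49 + 1) + (83 − 76 + 1) = 9 + 15 + 15 + 8 = 47 days.
- Uncovered: Days 1–9, 19–20, 36–48 and 64–75, which is 9 + 2 + 13 + 12 = 36 days.
- Check: 47 + 36 = 83.

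These are days of assessment, not days of last dose. An end-of-treatment ECG inside a window is still left out if it comes more than three days after the last intake.

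**4. An ambiguity that widens the gap**

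The SAP does not say whether an early ECG may be assigned to Day 28 or Day 56, where no ECG is planned. If it may go only to Day 14 or Day 84, covered days are 9 + 8 = 17 and uncovered days are 83 − 17 = 66.

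**5. From days to participants**

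This step cannot be taken. Neither document gives the number or timing of early stops, or of clinically indicated ECGs.

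**The case against.** **The SAP is silent; it does not delete the row.** Table layouts are in a separate document that was not available, the by-visit layout is stated only as a general rule, and the exclusion of unscheduled values is worded for by-visit tables. An any-time row could therefore exist and include them. This stands as a limit on certainty. But the protocol states the row, the SAP restates the table without it, and the same SAP section keeps it for laboratory data. The SAP should settle the matter itself.

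**Important cases are caught elsewhere.** New clinically relevant ECG findings are to be reported as adverse events (Protocol 7.1.2 and 8.3.3). The treatment-emergent tables are not by visit, run to 7 days after the last dose, and include events leading to discontinuation. Unscheduled values are listed, and individual ECG plots are planned. This stands and confines the harm to the summary counts. It does not repair the QTc tables, since a reading can fall in a QTc category without being judged clinically relevant.

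**The stakes are modest.** This is a small proof-of-concept study with descriptive ECG summaries, and Protocol 8.4.6 reports no interaction with cardiac ion channels and no clinically significant ECG findings in the two earlier studies for which it mentions them. The rules are the same in both arms. This stands and supports a low severity.

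**Stronger readings that the documents do not support**

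- *The SAP removed a QTc row.* The protocol's any-time entry covers ECG findings only. The QTc categories are an SAP addition, so nothing was dropped there; the table simply has the same gap.
- *Vital signs have the same defect.* Neither document plans a categorical vital-signs table, so there is no count to correct.
- *Repeat ECGs are excluded.* A poor-quality ECG is replaced (Protocol 8.3.3), and replicates at one visit are averaged (SAP 4.1.1).
- *36 of 83 days means that about 43% of early-stop ECGs are lost.* That requires stops spread evenly over time. A visit at which stopping is decided becomes the end-of-treatment visit, and scheduled visits with their ±2 or ±3 day tolerance lie inside the windows. Even spread may therefore overstate the loss.

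**Conclusion.** The point holds and is minor. As written, SAP 4.5.3 does not carry over the any-time-point entry that the protocol planned for ECG findings, gives none for the overall-interpretation and QTc tables, and leaves the omission undeclared in Section 4.8. Under the SAP's own default rules, clinically indicated ECGs and some early-stop ECGs do not enter these frequency counts, so the counts can miss a participant's worst on-treatment value.

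The size is unknown. The firm figure is that 36 of Days 1 to 83 fall in no visit window (66 if early ECGs can be assigned only to visits with a planned ECG). Depending on when participants stop, the loss of early-stop ECGs could be none or all of them.

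The conclusion assumes that the general rules in SAP 4.1.1 and 4.1.2 govern the ECG tables and that the separate table specifications do not already restore the row. If they do, only the SAP wording needs correcting. Laboratory counts are largely protected and are not part of this point.

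**What to change.** In SAP 4.5.3:

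1. Restore an any-time-point-during-treatment row in the ECG-findings table.
2. Add a worst post-baseline row, per participant, to the overall-interpretation table and to the QTc absolute and change category tables.
3. State that these rows use all ECGs from first dose to 7 days after last dose, including unscheduled and early end-of-treatment ECGs. This is the period the SAP already uses for treatment-emergent laboratory abnormalities.

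If the sponsor prefers by-visit tables only, declare and justify the departure from Protocol 9.3.3.2 in SAP 4.8.

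The cost is one row per table, from data already collected and listed. The by-visit rows stay as they are, and the question of which visit an early ECG belongs to no longer affects the overall counts.
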